Rationale: The Small Airways are a major site of obstruction in many respiratory diseases, including COPD. More insight into a diagnosis of Small Airways Dysfunction (SAD) in patients with COPD is clinically valuable as it might enable tailored pharmacotherapy. Currently, methods to diagnose SAD in COPD are not standardized and are not available in routine clinical practice. The Small Airways Dysfunction Tool (SADT) was developed to identify patients with asthma and SAD. Initially, the SADT included a comprehensive 63-item questionnaire. The number of items has been reduced to a SADT-asthma (SADT-a) questionnaire and key patient and disease characteristics for it to be feasible and implementable in clinical practice. Although there are many similarities between asthma and COPD, there might be differences in clinical characteristics and responses to small airways dysfunction between the two diseases.

The current study aims to adapt the original 63-item SADT questionnaire for dedicated use in COPD by reducing the number of items, and identifying COPD-SAD-specific items, to enhance its efficiency in identifying SAD when combined with key patient and disease characteristics in individuals with COPD (SADT-c). In addition, a comparison of diagnostic accuracy of spirometry and oscillometry will be made by interpretations by a panel of experts to provide a triage diagnosis. The previously developed machine learning AC/DC tool will be used to explore its diagnostic accuracy using oscillometry and spirometry results. This can contribute to standardizing oscillometry in clinical practice.

Objectives	Endpoints			
Primary				
1. To determine whether SADT-c can be used	The predictive value of SADT-c for detecting			
in patients with COPD to detect SAD.	SAD in patients with COPD.			
Secondary				
2. To determine whether the bronze model	Predictive value of SADT-a bronze model for			
SADT-a is predictive for SAD in COPD.	SAD in COPD.			
3. To develop SADT-c.	Agreement between SADT-c results and disease			
	parameters.			
	Content validity and reliability.			
4. To evaluate how SADT-c compares to SADT- a.	Relative predictive value of SADT-a versus SADT-c for SAD in COPD defined as R5–			
a.	$R_{20} > ULN^{1}$.			
5. To determine whether oscillometry and spirometry are equally effective for triage	Agreement between triage diagnoses from oscillometry and spirometry.			
	Relative usability of spirometry and oscillometry.			

Objective:

diagnosis in patients in primary care with respiratory symptoms.

Exploratory

Assess the diagnostic performance of the Asthma/COPD Differentiation Classification (AC/DC) Tool.

Diagnostic performance of AC/DC tool compared to expert panel diagnosis.

Study design: The study will take place in the Netherlands and aims to include 200 participants, targeting 50 with pre-existing COPD and 150 without diagnosis of which approximately 50 will be newly diagnosed with COPD. Participants, attending for usual or diagnostic care, will undergo an oscillometry test and complete a SADT-c questionnaire. The spirometry and oscillometry reports will be reviewed by a panel of experts (3-5 pulmonologists). In addition, 10-15 participants with COPD and SAD will be interviewed to assess if additional SADT-c questions are needed and to assess how participants process information to comprehend and respond to the question. If additional SADT-c questions are required, the questionnaire will be amended and completed by the same participants with COPD.

Study population: The study population will consist of patients referred by their General Practitioner (GP) when they are suspected to have asthma, COPD, asthma-COPD overlap (ACO) or when they present with pulmonary symptoms of unknown origin. Both patients invited for an initial diagnostic visit or a control visit can participate in the study.

Nature and extent of the burden and risks associated with participation, benefit and group relatedness: Participating in the SCOOP-study has minimal risks as it includes standard procedures, a non-invasive test, and a questionnaire. The study aims to assess if SADT-c can identify SAD in patients with COPD like SADT-a does in patients with asthma. It will conclude the test's suitability for COPD. Oscillometry, taking 45-60 seconds, could lessen the diagnostic burden and increase the access to lung function testing in primary care if proven equally effective.

1. INTRODUCTION AND RATIONALE

Chronic Obstructive Pulmonary Disease (COPD) is a leading cause of mortality and morbidity, imposing a high economic and social burden worldwide². It is characterized by obstructed airways and significant inflammatory process. This inflammation affects the entire respiratory tract, from the central to the peripheral airways that are less than 2mm in internal diameter, also known as the small airways³. The small airways can be affected by inflammation, remodeling, and changes in the surrounding tissue, all of which contribute to small-airways dysfunction. Small Airways Dysfunction (SAD) is the major site of obstruction in many respiratory diseases, including COPD^{4,5}.

SAD is a widely recognized feature of COPD that extensively contributes to irreversible airway obstruction and findings from ex vivo studies showed that loss of small airways precedes emphysema⁶. Moreover, in patients with COPD, SAD may increase lung hyperinflation and lead to clinical deterioration of health status. The small airways are a central treatment target, especially in patients with COPD⁷. Patients with SAD may benefit from treatment with extra-fine inhaled corticosteroids (ICS), with or without a long-acting β -agonist (LABA), which has been shown to improve lung function, airway responsiveness, symptoms, and exacerbation rates. Hence, more insight into a diagnosis of SAD in patients with COPD is clinically valuable as it might enable tailored pharmacotherapy⁸.

Currently, methods to diagnose SAD in COPD are not standardized and are not available in routine clinical practice⁹. The Small Airways Dysfunction Tool (SADT) was developed for patients with asthma as part of the ATLANTIS study, which utilized interviews, focus groups, and theories from research on patients with asthma, both with and without SAD¹⁰. Initially, the SADT included a comprehensive 63-item questionnaire, with items both suggestive (to include) and not suggestive for SAD (to exclude). After predictive modeling, and to be feasible and implementable in clinical practice, the number of items has been reduced to a SADT-a questionnaire⁸.

The SADT-a predicts SAD in patients with asthma using a single criterion – wheezing at rest – along with certain basic patient characteristics, such as age, sex, age at diagnosis, and Body Mass Index (BMI); this is the bronze model (area under receiver operation characteristic curve (AUC) 0.74 and positive likelihood ratio (LR+) 2.3). Its ability to accurately identify SAD in asthma is greatly enhanced with the use of spirometry, which evaluates lung function by measuring air volume and flow during breathing; this represents the silver model (AUC 0.87, LR+ 5.0). The results from spirometry primarily include the FEV_1 % predicted. The diagnostic precision further improves with the incorporation of oscillometry, marking the gold model (AUC 0.96, LR+ 12.8). This technique assesses lung function by measuring airflow resistance and includes parameters like the resistance difference between 5 and 20 Hz (R5-R20) and reactance area (AX)⁸.

The current study aims to adapt the original 63-item SADT questionnaire for dedicated use in COPD by reducing the number of items and enhance its efficiency in identifying SAD in individuals with COPD (the SADT-c). This process will follow the approach previously used for asthma⁸. We will assess the predictive value of SADT-c. Additionally, we will determine whether the bronze model of SADT-a is similarly predictive for SAD in COPD as is the bronze model of SADT-c.

Since oscillometry is not standardized in clinical practice, and the access and quality of spirometry is low¹¹, it would be of great value to determine whether oscillometry and spirometry are equally effective in the diagnostic work-up of respiratory symptomatic patients in primary care. Spirometry requires collaboration of the patient to perform a forced expiratory maneuver and well-trained Version 1.0, 19 April 2024 9 of 27

staff¹², whereas oscillometry is easy to perform as no training and limited effort of the patient is required (45 seconds of tidal breathing) and limited training of the staff¹³. In order to compare the effectiveness of spirometry and oscillometry, spirometry and oscillometry measurement will be interpreted by a panel of experts to provide a triage diagnosis. The previously developed machine learning AC/DC tool will be used to explore its diagnostic accuracy using oscillometry and spirometry results¹⁴.

2. OBJECTIVES

Primary Objective:

1. To determine whether SADT-c can be used in patients with COPD to detect SAD.

Secondary Objectives:

- 2. To determine whether the bronze model SADT-a is predictive for SAD in COPD.
- 3. To develop SADT-c.
- 4. To evaluate how SADT-c compares to SADT-a.
- 5. To determine whether oscillometry and spirometry are equally effective for triage diagnosis in patients in primary care with respiratory symptoms.

Exploratory Objective:

Assess the diagnostic performance of the Asthma/COPD Differentiation Classification (AC/DC) Tool.

3. STUDY DESIGN

The SCOOP-study will be executed in the Netherlands. The study consists of one visit during which all data will be collected. The aim is to include 200 participants in total. Of the 200 patients that will be seen for a visit, approximately 50 participants with previously diagnosed Chronic Obstructive Pulmonary Disease (COPD) and 150 participants without any diagnosis at the time of the visit will be invited. This should result in a total of 200 participants of which 100 are diagnosed with COPD: 50 with a pre-existing diagnosis and 50 newly diagnosed. An overview of the study flow is presented in figure 1.

Participants will visit the site for their usual care, which can be either a follow-up visit for those with an existing COPD diagnosis or a diagnostic visit. In addition to their usual care participants of the study will be asked to complete an oscillometry measurement and a Small Airway Dysfunction Tool for COPD (SADT-c) questionnaire. A panel of international experts will then review the oscillometry and spirometry reports of all 200 participants. Each report will be assessed by 3 to 5 independent pulmonologists in a randomized order. Finally, the triage diagnoses derived from oscillometry and spirometry assessments will be compared. The answers to the SADt-questionnaire items will be compared to the patients' respective SAD status to determine predictive value of SADT-c. Furthermore, ten to fifteen patients with COPD and SAD will be asked to participate in a cognitive interview to assess patient comprehension and necessity of additional questions. In case these are required, 100 COPD patients will be asked to complete the amended questionnaire.

[figure not shown]

Figure 1: Study flow for patients

4. STUDY POPULATION

4.1 Population (base)

The study population for the SCOOP study will consist of patients referred by their General Practitioner (GP) to the Asthma/COPD service. Patients can be referred by their GP when they are suspected to have asthma, Chronic Obstructive Pulmonary Disease (COPD), asthma-COPD overlap (ACO) or when they present with pulmonary symptoms of unknown origin. After referral by the GP, patients will be invited by the Asthma/COPD service. Both patients invited for an initial diagnostic visit or a control visit can participate in the SCOOP study.

4.2 Inclusion criteria

In order to be eligible to participate in this study, a participant must meet all of the following criteria:

- ≥35 years or older
- Suspected of having COPD, asthma or ACO as indicated by the referring GP **OR** a previous diagnosis of COPD

4.3 Exclusion criteria

A potential participant who meets the following criterium will be excluded from participation in this study:

• Inability to understand and sign the written informed consent form.

4.4 Sample size calculation

To determine whether Small Airway Dysfunction Tool for COPD (SADT-c) can be used in patients with COPD to detect Small Airways Disease (SAD) a prediction model will be used. To estimate the required sample size for a prediction study, a well-known rule of thumb is to ensure at least 10 events for each predictor parameter.

Previous studies indicated a prevalence of SAD in patients with COPD ranging from $74\%^{15}$ to $83\%^{16}$. The final prediction model previously developed for patients with asthma included four variables in the bronze model and 7 variables in the gold model⁸. Therefore, we assume that we will have enough statistical power when we include 100 patients diagnosed with COPD in the current study.

5. SCOOP procedures

The SCOOP study will be integrated in the visits of the Asthma/COPD service for primary care at the study sites. General Practitioners (GPs) can refer individual patients (≥18 years of age) who are suspected to have obstructive airway disease (OAD) such as asthma, Chronic Obstructive Pulmonary Disease (COPD), asthma-COPD overlap (ACO) or present with pulmonary symptoms of unknown origin¹⁷. Visits can be for initial diagnosis of the OAD or for (yearly) follow-up of the disease.

In preparation for the regular asthma/COPD service visit the patient will receive questionnaires to complete, i.e.: the Asthma Control Questionnaire (ACQ), the Clinical COPD Questionnaire (CCQ) and a medical history questionnaire assessing gender, age, age of onset, family history, symptoms, exacerbations (oral corticosteroids or antibiotics use), allergy and other stimuli-provoking symptoms, medication, occupation, and smoking history.

During the visit the patient is assessed by a trained lung function technician. The following measurements are collected: Body mass index (BMI), evaluation and if needed instruction of inhalation technique (according to the Dutch Inhalation Medication Instruction School guidelines), spirometry (according to international guidelines).

Besides the regular assessments, the following assessments will be added for the SCOOP-study:

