5.1 Small Airways Dysfunction Tool (SADT) questionnaire

The SADT questionnaire was developed for patients with asthma and consist of 63 items. SADT items were scored on a 3-point scale (no, yes, unknown)¹⁰. The items reflect specific signs and symptoms which could be suggestive for Small Airways Dysfunction (SAD) or could reflect signs and symptoms that are suggestive for less SAD.

A shorter version of the SADT for asthma with items more tailored to COPD patients will be devised as a part of study. Input from the scientific advisory board (in part the steering committee of the ATLANTIS study¹⁸.) and patient interviews (described in chapter 5.4) will be used. The SADT for COPD (SADT-c) will contain approximately 15 questions.

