8.1 Primary study parameter(s)

The primary endpoint is the predictive value of SADT-c for SAD in COPD. The statistical hypothesis for the primary objective is that the predictive value of SADT-c is above the lower limit of the confidence interval of predictive value of SADT-a (AUC 0.74, LR+ 2.3 for the SADT-a bronze model). The hypothesis will be tested at a 2-sided significance level of 0.05.

For the analysis of this primary endpoint, the following population is defined:

- All participants that have a prior or novel COPD (triage) diagnosis, and
- Do not have an asthma, asthma-COPD overlap syndrome, missing or other diagnosis, and
- Have filled in the SADT-c questionnaire.

The presence of SAD will be based on oscillometry results. A resistance difference between 5 and 20 Hz (R5-R20) cutoff of 0.07 kPa x s x L⁻¹ will be used to define the presence of SAD¹⁵.

Analysis will be performed as done earlier for the development of SADT for asthma⁸. In short, to assess the predictive value of SADT-c we first will select the most important SADT items (secondary study parameter). Regression analysis will be used to select SADT items that show a relation with SAD in the expected direction based on the content validity of the items. In a next step the most important SADT items for SAD group will be selected by using logistic regression models. Prediction models using bootstrapping resampling will be used. In addition to the individual SADT items, also patient characteristics, such as age, sex, and height, BMI, will be considered as independent predictors in the model.

Selected key SADT items will be used together with available clinical information to build logistic regression models to predict the SAD group. Three levels of clinical information will be considered resulting in three regression models:

- Bronze: Basic patient characteristics (such as age, sex, age at diagnosis, BMI, or other)
- Silver: Spirometry test results (FEV₁ % predicted)
- Gold: Oscillometry test results (R5-R20 and reactance area (AX)).

For each model the area under the receiver operating characteristic curve (AUC), positive likelihood ratio (LR+) and sensitivity and specificity will be calculated, using a probability cut-off of 0.5 to indicate predicted SAD.

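### Section 4.4 claims adequate power at 100 COPD patients from an events-per-predictor rule, which gives no power for the primary test in section 8.1

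*Protocol*

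**What the plan says.** Protocol section 4.4 sizes the study for a prediction model by stating that "a well-known rule of thumb is to ensure at least 10 events for each predictor parameter". It adds two inputs. The first is SAD prevalence: "Previous studies indicated a prevalence of SAD in patients with COPD ranging from" 74% to 83%. The second is the size of the asthma models, which "included four variables in the bronze model and 7 variables in the gold model". From these it concludes: "Therefore, we assume that we will have enough statistical power when we include 100 patients diagnosed with COPD in the current study". No AUC, reference limit, alpha or target power enters the argument.

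Section 8.1 then states the primary hypothesis, that the "predictive value of SADT-c is above the lower limit of the confidence interval of predictive value of SADT-a", and gives AUC 0.74 and LR+ 2.3 for the SADT-a bronze model. It adds: "The hypothesis will be tested at a 2-sided significance level of 0.05". The numeric lower limit for SADT-a appears nowhere in the protocol, and neither does an expected AUC for SADT-c.

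Section 3 shows where the 100 come from: "This should result in a total of 200 participants of which 100 are diagnosed with COPD: 50 with a pre-existing diagnosis and 50 newly diagnosed".

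**The concern.** The conclusion in 4.4 does not follow from its premises. An events-per-predictor count guards against overfitting when a model is built. It says nothing about the chance that a test against a fixed limit succeeds, and it would say nothing even if the count were beyond dispute.

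This matters because the study is meant to settle a question: section 9.3 says that the analyses will decide whether the tool applies to COPD. If SADT-c performs in COPD as SADT-a does in asthma, the test could well be non-significant simply because 100 patients estimate an AUC imprecisely. A reader who trusts the assurance in 4.4 could take that result as evidence against the tool.

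The point is not that detail has been left to the SAP. The protocol itself makes the power claim, and a later SAP cannot make the inference valid.

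**Working it through.** **1. What 4.4 delivers.** With SAD as the event and 7 predictors, the rule needs 10 × 7 / 0.74 = 95 patients, or 10 × 7 / 0.83 = 85. So 100 satisfies the rule on that count. No power figure is stated, so there is none to reproduce.

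**2. Inputs for the 8.1 test.**
- From the protocol: 100 COPD patients; 74 SAD and 26 non-SAD, or 83 and 17; two-sided alpha 0.05; reference AUC 0.74.
- Assumed: the bronze AUC is the deciding measure; the true SADT-c AUC, A, is 0.74; the SADT-a lower limit, L, is varied from 0.58 to 0.72.

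**3. Standard error (Hanley-McNeil).** Var = [A(1−A) + (n1−1)(Q1−A²) + (n0−1)(Q2−A²)] / (n1·n0), where n1 is the SAD count, n0 the non-SAD count, Q1 = A/(2−A) and Q2 = 2A²/(1+A). At A = 0.74, Q1−A² = 0.0397 and Q2−A² = 0.0818.
- 74/26: (0.192 + 73 × 0.0397 + 25 × 0.0818) / 1924 = 0.00267, so SE = 0.0517 and the 95% half-width is 0.101.
- 83/17: (0.192 + 82 × 0.0397 + 16 × 0.0818) / 1411 = 0.00337, so SE = 0.0581 and the half-width is 0.114.

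**4. Power** = Φ((A − L)/SE − 1.96). For example, at L = 0.68 with 74/26: 0.06/0.0517 − 1.96 = −0.80, which gives 21%. The last two columns come from a binormal simulation with DeLong intervals (at least 4,000 samples per setting).

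| L | 74/26 | 83/17 | Simulated 74/26 | Simulated 83/17 |
|---|---|---|---|---|
| 0.58 | 87% | 79% | 77% | 66% |
| 0.60 | 77% | 67% | 69% | 56% |
| 0.62 | 64% | 54% | 57% | 46% |
| 0.64 | 49% | 41% | 45% | 37% |
| 0.68 | 21% | 18% | 23% | 21% |
| 0.70 | 12% | 10% | 15% | 15% |
| 0.72 | 6% | 5% | 9% | 9% |

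The SE in simulation is about 0.056-0.067, a half-width of 0.11-0.13. The simulated power is higher at 0.70-0.72 partly because the DeLong lower bound exceeded the true AUC in about 5.6% of samples instead of 2.5%.

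**5. Limit needed for 80% power.** L = 0.74 − 2.80 × SE, which is 0.595 (74/26) or 0.577 (83/17). By simulation it would have to be lower still.

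**6. A check that needs no value of L.** At a true AUC of 0.74, power exceeds 50% only if 0.74 − L exceeds 1.96 SE, that is, if the lower arm of the SADT-a interval is wider than the half-width expected here. For 80% it must be 2.80/1.96 = 1.43 times as wide. With the same class balance this implies a SADT-a sample of about 100/1.43² = 49; over assumed SAD shares of 30-83% it is about 60 or fewer.

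**7. If SADT-c is better than SADT-a.** At a true AUC of 0.80 the SE is 0.0449 (74/26) or 0.0497 (83/17). Power is 95% / 90% at L = 0.64 but 60% / 52% at L = 0.70.

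**The case against.** The strongest reply is that the two inputs that drive power are not in the protocol. The SADT-a limit is in a cited source, and SADT-c is tailored to COPD (section 5.1: "The SADT for COPD (SADT-c) will contain approximately 15 questions"), so a true AUC equal to SADT-a's is not the protocol's assumption. Section 8.1 also fits silver and gold models, names LR+ beside the AUC, and does not say which decides. All of this stands. A reader might infer that the test simply has 5-50% power, or that SADT-c will usually fail. The protocol does not support that: the range holds only for a limit of about 0.64-0.72 with a true AUC of 0.74. At limits of 0.60-0.62 power is 54-77%, and a better tool would do better.

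A reader might also infer that success means only that the SADT-c point estimate exceeds the limit, so that the error rate is near 50% when the true AUC equals it. The text does not read that way: a bare comparison of estimates is not a test at the 0.05 level.

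It can be added that 4.4 only assumes power, openly from a rule of thumb, and that no computed figure is wrong. That is fair: this is a mismatch between sizing basis and hypothesis. Nor does a non-significant primary test by itself trigger any action: section 8.2 adds interview-derived items only when predictive value is significantly reduced against SADT-a.

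Finally, the calculation omits item selection in the same data, which if uncorrected would raise the observed AUC and the pass rate. It also omits withdrawals, exclusions and any shortfall in the 50 expected new diagnoses, which would lower power. None of these points supplies a basis for the claim in 4.4.

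**Conclusion.** The concern holds in a conditional form. The assurance in 4.4 is unsupported, because the rule it rests on yields no power for the 8.1 test. Whether power is in fact adequate cannot be settled from the protocol. If the bronze AUC decides and is truly 0.74, power is below 80% for any SADT-a limit above about 0.58-0.60, and a limit that low would imply a very small SADT-a sample. Adequate power therefore depends on SADT-c being clearly better than SADT-a: for limits of 0.64-0.72, 80% power needs a true AUC of about 0.775-0.84. This should be corrected before the analysis, but it is a matter of stating what the design delivers and does not invalidate the study.

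**What to change.** In 4.4, replace the power claim with two statements: the expected 95% confidence interval half-width for the AUC at 100 COPD patients (about 0.10-0.11, up to about 0.13 by simulation), and the power of the 8.1 test, computed with the numeric SADT-a limit and a stated expected AUC for SADT-c.

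In 8.1, state that limit, and state that the criterion is the lower bound of the SADT-c AUC confidence interval exceeding it. Report the AUC with its 95% confidence interval as the primary result. An interval that contains the limit should be read as inconclusive; one that lies wholly below it is evidence against the tool. Calling every failed test inconclusive would go too far, since it would leave the hypothesis with no negative outcome.

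The cost is rewording two sections and one short calculation. The downside is a less favourable stated power. No extra patients are proposed. Powering the test at 80% for a true AUC of 0.74 would take 257-324 COPD patients at a limit of 0.65 and 1,293-1,631 at 0.70 (same formula), so stating the precision honestly is the practical course.

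### Section 4.4's events-per-parameter rule supports 4 to 7 variables only if SAD patients are counted; the limiting class is the 17-26 expected non-SAD patients, enough for 1-2 parameters

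*Protocol*

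**What the plan says.** Protocol section 4.4 bases the sample size on one heuristic: "a well-known rule of thumb is to ensure at least 10 events for each predictor parameter". It cites earlier studies that put SAD prevalence in COPD at 74% to 83%, and notes that the final asthma models "included four variables in the bronze model and 7 variables in the gold model". From these it concludes: "Therefore, we assume that we will have enough statistical power when we include 100 patients diagnosed with COPD in the current study". It does not say which outcome class is the event, gives no event count and does not mention patients without SAD.

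Two other places determine how many parameters are in play. Section 5.1 states: "The SADT for COPD (SADT-c) will contain approximately 15 questions". It describes the source questionnaire in these terms: "SADT items were scored on a 3-point scale (no, yes, unknown". Section 8.1 selects items by their regression relation with SAD, then by logistic regression. It adds that "also patient characteristics, such as age, sex, and height, BMI, will be considered as independent predictors in the model", and age at diagnosis appears in its bronze model. Section 8.1 also plans bootstrap resampling, without saying what is resampled or for what purpose.

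**The concern.** A rule of this kind, applied to a binary logistic model, concerns the rarer outcome class. Swapping the labels SAD and non-SAD only reverses the signs of the coefficients, so the majority cannot supply information that the minority lacks. With SAD in about three quarters or more of COPD patients, the scarce group is those without it.

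The rule also concerns the parameters that are tried. When items are chosen by their association with the outcome in the patients used to fit the model, every candidate uses information, including those later discarded.

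The primary endpoint is at stake. The AUC depends on both classes. Specificity, and through it LR+, is estimated from the non-SAD patients alone. A model built from many candidates and few non-SAD patients risks an unstable item set and an apparent accuracy that is too high. Section 8.1 compares that accuracy with the lower confidence limit for SADT-a, whose bronze model has an AUC of 0.74 and an LR+ of 2.3.

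**Working it through.** **Inputs.** From section 4.4: N = 100 with COPD, SAD prevalence 74% to 83%, 10 events per parameter, planning sizes of 4 and 7 variables. From sections 5.1, 6.1.1 and 8.1: about 15 questions, plus age, sex, height, BMI and age at diagnosis, so about 15 + 5 = 20 candidates. The 20 is a reconstruction; the protocol gives no total.

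**1. Reproducing the plan's conclusion.** Parameters supported = N × class share / 10. With SAD as the event:

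- 100 × 0.74 = 74 events, 74/10 = 7.4 parameters
- 100 × 0.83 = 83 events, 83/10 = 8.3 parameters

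This covers 7 variables. Solving for N gives 70/0.74 = 94.6, so 95, or 70/0.83 = 84.3, so 85; 100 exceeds both. Counting SAD patients as events therefore reproduces the statement.

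**2. The same rule on the smaller class.**

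- 100 × (1 − 0.74) = 26 non-SAD, 26/10 = 2.6 parameters
- 100 × (1 − 0.83) = 17 non-SAD, 17/10 = 1.7 parameters

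In whole parameters this is 1 to 2.

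**3. Patients per parameter at N = 100, and N needed for 10 per parameter.** N needed = 10 × parameters / non-SAD share, rounded up.

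| Parameters | Non-SAD each (83%; 74%) | SAD each (74%; 83%) | N needed, non-SAD limiting (74%; 83%) |
|---|---|---|---|
| 4 | 17/4 = 4.3; 26/4 = 6.5 | 18.5; 20.8 | 40/0.26 → 154; 40/0.17 → 236 |
| 7 | 17/7 = 2.4; 26/7 = 3.7 | 10.6; 11.9 | 70/0.26 → 270; 70/0.17 → 412 |
| 20 candidates | 17/20 = 0.85; 26/20 = 1.3 | 3.7; 4.2 | 200/0.26 → 770; 200/0.17 → 1177 |

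The candidate row is below 10 whichever class is counted. It would be lower still if the third answer category were kept as a level, since each question could then use two parameters.

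**4. Could chance or another prevalence rescue it?** Four variables need 40 non-SAD patients. The binomial probability of at least 40 in 100 is about 0.0015 at 74% prevalence and below 0.000001 at 83%. At 50%, the most favourable prevalence possible, the smaller class is 50, or 5 parameters: enough for four, not for seven.

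**5. What 100 patients give in precision.** Hanley-McNeil standard error for AUC A with n₁ SAD and n₀ non-SAD patients:

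SE² = [A(1 − A) + (n₁ − 1)(P₁ − A²) + (n₀ − 1)(P₂ − A²)] / (n₁n₀), where P₁ = A/(2 − A) and P₂ = 2A²/(1 + A).

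At A = 0.74: A² = 0.5476, P₁ = 0.5873, P₂ = 0.6294.

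- 74 and 26: SE = 0.052, half-width 1.96 × SE = 0.10, interval about 0.64 to 0.84
- 83 and 17: SE = 0.058, half-width 0.11, interval about 0.63 to 0.85

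This is for a score fixed in advance. It leaves out the uncertainty added by choosing items in the same data.

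**The case against.** The strongest reply is that section 4.4 offers a planning heuristic and that much of the criticism supplies what the protocol does not say. It never states that SAD patients were the events; that is inferred. Applying the rule to the rarer class and to candidates is standard methodology, not protocol text. The four and seven variables are sizes of asthma models; no size is fixed for SADT-c. The 17-26 depends on cited prevalences, and sections 6.1.1 and 8.1 define SAD differently (an upper limit of normal against a 0.07 cut-off), so the realised split may differ. The gold model includes R5-R20, the measure that defines SAD, so 270-412 is only what the rule would imply and not a useful target.

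These points stand as qualifications, but they do not restore the conclusion. No other reading of an event lets 100 patients cover seven variables, and the candidate set fails under either reading.

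A reader might also infer that section 8.1 uses unpenalised stepwise selection with uncorrected accuracy. The document does not support this. It describes a screen on the expected direction followed by logistic regression, names neither a stepwise algorithm nor the type of estimation, and does plan bootstrapping. Section 8 leaves technical detail to the statistical analysis plan. The bootstrap can measure and correct optimism if it repeats the selection, but it adds no non-SAD patients and so does not repair section 4.4.

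**Conclusion.** The adequacy statement in section 4.4 is wrong as written. At the protocol's own prevalence, 100 COPD patients are expected to include 17-26 without SAD. At 10 per parameter they support 1-2 parameters, against the 4 to 7 used for planning and about 20 candidates.

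This rests on three assumptions: that the rule applies to the smaller class of a binary logistic model, that the cited 74-83% holds in this population, and that the reconstructed candidate count is about right. The first is standard. The second matters in degree: a prevalence near 50% would satisfy the rule for a four-variable model, but no prevalence would for seven. The third could be off by several without changing the result.

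A reader might go further and conclude that the study must be enlarged or that its reported accuracy will necessarily be inflated. Neither follows. A study of 100 can serve as model development if its precision and optimism are stated honestly, and the protocol does not give enough detail to put a size on any optimism.

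**What to change.** Keep n = 100 and make these changes.

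- **Section 4.4:** define the event, and state the expected smaller class (17-26, conditional on the cited prevalence) and the number of candidate parameters. Withdraw the statement that power is sufficient. Replace it with the expected precision: a 95% half-width of about ±0.10-0.11 at an AUC of 0.74 for a fixed score, described as a best case that ignores item selection.
- **Section 8.1:** describe the result as model development. Specify that the planned bootstrap repeats the entire item selection in each resample, and that optimism-corrected AUC and LR+ are reported. Penalised or shrunken estimation on an item list shortened before the outcome is examined is a suitable option, not the only one.

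The cost is protocol and analysis-plan wording plus some computing. No patients, visits or measurements are added. The price is a less favourable claim about what 100 patients can establish.
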